7.3 Safety/Tolerability

Analyses will be performed for all patients having received at least one dose of study drug. The study will use the CTCAE version 5.0 for reporting of non-hematologic adverse events.

8.0 ADVERSE EVENTS

8.1 Experimental Therapy

For the most recent safety update, please refer to the current Investigator's Brochure or Study Agent Prescribing Information.

8.1.1 Special Warnings and Precautions for Use

Contraception:

Subjects receiving IONIS-AR-2.5_{RX} are advised to use two acceptable (to treating investigator) methods of birth control (one of which must include a condom as a barrier method of contraception) starting at the time of informed consent and continuing throughout the course of treatment and for at least 120 days after last dose of trial therapy.

8.2 Adverse Event Reporting Requirements

Adverse event (AE) monitoring and reporting is a routine part of every clinical trial and is done to ensure the safety of subjects enrolled in the studies as well as those who will enroll in future studies using similar agents. Data on adverse events will be collected from the time of the initial study treatment administration or intervention through 30 days after the last dose of study treatment or study intervention. Any serious adverse event that occurs more than 30 days after the last study treatment or intervention and is considered related to the study treatment or intervention must also be reported. Serious Adverse Events (SAEs) will continue to be followed until:

- Resolution or the symptoms or signs that constitute the serious adverse event return to baseline;
- There is satisfactory explanation other than the study treatment or intervention for the changes observed; or
- Death.

The investigator is responsible for the detection, documentation, grading and assignment of attribution of events meeting the criteria and definition of an AE or SAE. The definitions of AEs and SAEs are given below. It is the responsibility of the principal investigator to ensure that all staff involved in the trial is familiar with the content of this section.

Any medical condition or laboratory abnormality with an onset date before initial study treatment administration or intervention is considered to be pre-existing in nature. Any known pre-existing conditions that are ongoing at time of study entry should be considered medical history.

All events meeting the criteria and definition of an AE or SAE, as defined in Section 8.3, occurring from the initial study treatment administration or intervention through 30 days following the last dose of the study treatment or study intervention must be recorded as an adverse event in the patient's source documents and on the CRF regardless of frequency, severity (grade) or assessed relationship to the study treatment or intervention.

In addition to new events, any increase in the frequency or severity (i.e., toxicity grade) of a pre-existing condition that occurs after the patient begins study treatment or intervention is also considered an adverse event.

8.3 Definitions

8.3.1 Adverse Event

An adverse event (AE) is any untoward medical occurrence in a patient receiving study treatment and which does not necessarily have a causal relationship with this treatment. An AE can be any unfavorable and unintended sign (including an abnormal laboratory finding), symptom, or disease temporally associated with the use of an experimental intervention, whether or not related to the intervention.

- *Diagnostic and therapeutic non-invasive and invasive (i.e., surgical) procedures will not be reported as adverse events. However, the medical condition for which the procedure was performed must be reported if it meets the definition of an adverse event unless it is a pre-existing (prior to protocol treatment) condition.*
- *Abnormal laboratory values or test results constitute adverse events if they induce clinical signs or symptoms or require therapy. They are to be captured under the signs, symptoms or diagnoses associated with them.*

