Patients in the current phase II trial will receive low dose aspirin (81 mg) daily while receiving study drug to mitigate the apparent increased risk of VTE.

Clotting and bleeding functions including platelet counts will be closely monitored on this study including weekly CBCPD, PT/PTT/INR and reviewed continuously as well at the interim analysis time points. If so needed and indicated by the data, including at interim safety analysis and continually by the Data and Safety Monitoring Board, we would modify the above strategy towards either escalating the prophylactic anti-coagulation to enoxaparin 40 mg daily, for example, or removing the 81 mg daily dose of aspirin.

5.1.2 Upon enrollment, each patient will be assigned a dose level from the statistician to initiate treatment. (See Section 11 for further details.)

Assigned Dose level (TITE-CRM):

Assigned Dose Level	Enzalutamide Dose	IONIS-AR-2.5 _{Rx} Dose
3	160 mg	900 mg
2	160 mg	750 mg
1	160 mg	600 mg

5.1.3 Definition of Dose Limiting Toxicity (DLT):

Excessive toxicity/dose limiting toxicity (DLT) will be defined as any Grade 3 or higher toxicity (as defined by CTCAE v5.0) that occurs during the DLT evaluation period (2 cycles plus labs prior to start of cycle 3). Toxicity that is clearly and directly related to the primary disease or to another etiology is excluded from this definition. The following will be DLTs:

- Liver transaminase elevation Grade 2 lasting 14 calendar days or more OR Liver transaminase elevation Grade 3 or 4
- Grade 3 or Grade 4 febrile neutropenia will be a DLT regardless of duration or reversibility
- Grade 3 thrombocytopenia that IS associated with clinically significant bleeding that requires medical intervention

The DLT Definition excludes the following conditions:

- Grade 3 fatigue lasting ≤ 7 days
- Grade 3 endocrine disorder (thyroid, pituitary, and/or adrenal insufficiency) that is managed with or without systemic corticosteroid therapy and/or hormone replacement therapy and the subject is asymptomatic
- Grade 3 infusion-related reaction (first occurrence and in the absence of steroid prophylaxis) that resolves within 6 hours with appropriate clinical management
- Grade 3 or 4 lymphopenia
- Grade 3 or 4 neutropenia that is not associated with fever or systemic infection that improves within 7 days
- Grade 3 thrombocytopenia that is not associated with clinically significant bleeding that requires medical intervention, and improves by at least 1 grade within 3 days

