11.2.2 Definition of Secondary Endpoints

The secondary endpoints of efficacy are radiographic progression-free survival time (rPFS) by PCWG3-modified RECIST 1.1, 30% PSA reduction from baseline, PSA progression-free survival time, duration of therapy (DOT), duration of PSA Response (DOR), progression-free survival time and overall survival time.

The secondary endpoints for safety and toxicity are adverse events as assessed by CTCAE criteria 5.0 and classified by body system, grade, and attribution. Other toxicity endpoints include intrapatient dose delays and dose reductions.

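### Section 8.3.1 gives two rules for laboratory adverse events; under the narrower one, asymptomatic transaminase rises, some of them DLTs, would be missing from the AE table

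*Combined protocol and SAP*

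**What the plan says.** Section 8.3.1 opens with a broad definition: "An AE can be any unfavorable and unintended sign (including an abnormal laboratory finding), symptom, or disease temporally associated". It attaches no condition to the laboratory finding. The second bullet under it is narrower: "Abnormal laboratory values or test results constitute adverse events if they induce clinical signs or symptoms or require therapy". The bullet then says how such values are recorded: "They are to be captured under the signs, symptoms or diagnoses associated with them".

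Section 8.2 makes this definition decide what is collected. What must go into the source documents and onto the CRF is "All events meeting the criteria and definition of an AE or SAE, as defined in Section 8.3".

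Section 5.1.3 defines the liver DLT by grade and duration alone: "Liver transaminase elevation Grade 2 lasting 14 calendar days or more OR Liver transaminase elevation Grade 3 or 4". The tables in Section 5.2.1 likewise act on grade or count when they call for IONIS-AR-2.5Rx to be interrupted, reduced or discontinued.

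In Section 11.2.2 the first part of the secondary safety endpoint is "adverse events as assessed by CTCAE criteria 5.0 and classified by body system, grade, and attribution". The second part is intrapatient dose delays and reductions. Section 11.6.2 reports the AEs as counts and proportions and describes delays and reductions by starting dose level. It names no laboratory-grade or shift table.

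**The concern.** The liver is where this trial most needs a clean graded record. Section 1.3 reports that the dose-limiting toxicity in the earlier single-agent study was a rise in liver function tests at 900 mg. Section 9.1 describes a trend in ALT, AST and ALP at 600 mg and 900 mg, which are dose levels 1 and 3 here. Appendix E records that the DLT definition was amended to add Grade 2 transaminase toxicity after two patients at dose level 3 had toxicity.

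A transaminase rise is often only a laboratory finding. If the bullet governs, a patient could have a DLT, or stop IONIS-AR-2.5Rx for a liver rise, with no matching line in the AE table. That table would then disagree with the DLT count and understate liver toxicity by dose level. If the two sites read Section 8.3.1 differently, it would also mix two recording rules. The monthly data review in Section 13.0 follows safety through SAE and AE reporting, so the same gap could reach the reports sent to the DSMC.

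**Working it through.** No sample size, power or alpha figure depends on this point, so there is no figure in the plan to reproduce. The check is a comparison of the passages, followed by a scale calculation.

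**Step 1: the two rules applied to one case.** Take a patient with a Grade 3 ALT rise in cycle 2, no symptoms and no treatment beyond a hold of study drug.
- Opening sentence of 8.3.1: the rise can be an AE.
- Bullet in 8.3.1: the rise causes no sign or symptom and, on an ordinary reading, a hold is not therapy. The condition is not met, and there is no associated sign, symptom or diagnosis to record it under.
- Section 5.1.3: the rise is a DLT unless clearly due to the disease or another cause.
- Section 5.2.1: dosing is interrupted.

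So under the bullet the patient has a DLT and a hold but no AE entry.

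**Step 2: what other records would show.**
- *DLT record.* Section 12.0 requires DLT information within one business day, so the primary toxicity endpoint does not depend on Section 8.3.1. It covers only the DLT window (two cycles, 42 days, plus the laboratory tests before cycle 3). Section 9.1 says the elevations tended to develop slowly, and the synopsis anticipates a median of 12 months on therapy. A rise after the window cannot be a DLT, and the AE table is the only planned summary of its grade.
- *Delays and reductions.* These would register the hold or reduction, but Section 11.6.2 states no breakdown by cause or grade. Under Section 5.2.1, a Grade 4 transaminase rise, or a transaminase rise with the specified concurrent bilirubin elevation, leads to discontinuation, which is neither a delay nor a reduction.
- *Laboratory data.* The Time and Events Table in Section 6.0 schedules the CBC and the metabolic panel (ALT, AST and total bilirubin included) at every infusion visit. The data will exist, but no table of them is planned.

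**Step 3: an example in the documents.** Section 9.1 describes a patient in the earlier study with Grade 2 ALT and Grade 1 AST at Cycle 2 Day 8. Treatment was held and the values were normal a week later; no symptom or therapy is mentioned. Here such a rise would fall short of the 14-day Grade 2 DLT criterion but would call for interruption under Section 5.2.1. Under the bullet it would not be an AE.

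**Step 4: scale for DLTs only.** Inputs are 1 liver DLT in 13 patients at 900 mg (Section 1.3), up to 35 patients (Section 11.3), and a share *s* of liver DLTs that are asymptomatic and untreated. The documents do not give *s*, so it is run from 0 to 1.
- Rate: 1/13 = 7.7%, exact 95% CI 0.2% to 36.0%.
- Expected liver DLTs: 35 × 1/13 = 2.7.
- Probability of at least one: 1 − (12/13)^35 = 0.94.
- Expected liver DLTs missing from the AE table under the bullet: 35 × (1/13) × *s*.

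| *s* | Expected missing |
|---|---|
| 0 | 0 |
| 0.25 | 0.7 |
| 0.5 | 1.3 |
| 0.75 | 2.0 |
| 1 | 2.7 |

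This shows scale and is not an estimate. The 1/13 comes from single-agent treatment on a different schedule, it is applied to all 35 patients as if all received 900 mg, and its interval is wide. Laboratory-only holds that are not DLTs, and rises after the window, are not counted.

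**The case against.** A reader might infer that the protocol excludes asymptomatic laboratory changes from the AEs outright. It does not. The bullet says *if*, not *only if*, and the opening sentence of the same section points the other way. Other sections also treat liver-enzyme rises as adverse events. The hepatic rule for enzalutamide in Section 5.2.2 counts 28 days from the onset of the adverse event, meaning the rise itself. Section 9.1 lists raised ALT and AST among the AEs of the earlier study and asks for liver effects to be followed through both AE recording and chemistry. Section 5.2 has toxicity graded by CTCAE 5.0 in every treated patient. The likely intent is that such rises are recorded. This all stands, and it is why the fault is an inconsistency and not a settled exclusion.

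A reader might also infer that these events drop out of the secondary safety endpoint as a whole, or that the DLT count is compromised. Neither follows: delays and reductions remain part of the endpoint, and DLTs are a primary endpoint with their own entry rule.

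Third, it is tempting to say that most liver DLTs would be lost. Nothing in the documents gives the asymptomatic share, and zero is within the range. Extending the claim to haematologic DLTs is weaker still. The listed ones require fever or clinically significant bleeding, and several uncomplicated cytopenias are excluded.

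The objection does not remove the difficulty that the bullet serves a purpose only if it restricts, and that it is the more specific of the two sentences. A site could follow it in good faith, and nothing in Section 8.2 or 11.6.2 would correct the result.

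**Conclusion.** The point holds as an internal inconsistency in Section 8.3.1 with a consequence that depends on which sentence a site follows. Under the bullet, asymptomatic and untreated transaminase rises would be missing from the AE-count component of the secondary safety endpoint. That covers rises that are DLTs, rises that change or stop dosing, and rises after the DLT window. No planned laboratory table would show them.

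The DLT count, the MTD estimate and the delay and reduction summaries are unchanged. The loss ranges from none to all of the asymptomatic liver events and cannot be narrowed from the documents. The conclusion rests on two assumptions: that at least one site applies the bullet as a restriction, and that some liver rises are asymptomatic and untreated. The fault matters because it falls on the drug's known liver signal and is cheap to remove.

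**What to change.** 1. In Section 8.3.1, reconcile the two sentences. State that a laboratory abnormality is also recorded as an AE, with its own CTCAE term and grade, when it meets a DLT criterion or leads to a hold, reduction or discontinuation of study drug. This need not extend to every Grade 3 value, some of which the DLT definition sets aside.
2. In Section 11.6.2, add a table of worst post-baseline CTCAE grade by assigned dose level for ALT, AST, bilirubin, neutrophils and platelets, from the laboratory tests already scheduled in Section 6.0. Neutrophils and platelets belong in it because Section 5.2.1 acts on those counts directly.

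The cost is one clause, slightly more AE entries and one more table. No patient procedure is added and no dosing or clinical rule changes.

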8.3.2 Serious Adverse Event

An adverse event is considered “serious” if, in the view of the sponsor investigator, it results in any of the following outcomes:

- Death
If death results from (progression of) the disease, the disease should be reported as event (SAE) itself.
- A life-threatening adverse event
An adverse event is considered ‘life-threatening’ if, in the view of either the investigator [or sponsor], its occurrence places the patient or subject at immediate risk of death. It does not include an adverse event that, had it occurred in a more severe form, might have caused death.
- Inpatient hospitalization or prolongation of existing hospitalization for ≥ 24 hours.
- A persistent or significant incapacity or substantial disruption of the ability to conduct normal life functions
- A congenital anomaly/birth defect
- Important medical event
Any event that may not result in death, be life-threatening, or require hospitalization may be considered serious when, based upon appropriate medical judgment, they may jeopardize the patient and may require medical or surgical intervention to prevent one of the outcomes listed in this definition of “Serious Adverse Event”. Examples of such medical events include allergic bronchospasm requiring intensive treatment in an emergency room or at home; convulsions that do not result in inpatient hospitalization or the development of drug dependency or drug abuse.

Previously planned (prior to signing the informed consent form) surgeries should not be reported as SAEs unless the underlying medical condition has worsened during the course of the study. Preplanned hospitalizations or procedures for preexisting conditions that are already recorded in the patient’s medical history at the time of study enrollment should not be considered SAEs. Hospitalization or prolongation of hospitalization without a precipitating clinical AE (for example, for the administration of study therapy or other protocol-required procedure) should not be considered SAEs. However, if the preexisting condition worsened during the course of the study, it should be reported as an SAE.

- Procedure in case of Pregnancy
If during the conduct of the clinical trial, a male subject impregnates his partner, the subject should report the pregnancy to the investigator. The investigator should report the pregnancy to the Coordinating Center as an SAE within 24 hours of awareness of the event. The expected date of delivery or expected date of the end of the pregnancy, last menstruation, estimated fertility date, pregnancy result and neonatal data etc., should be included in this information.

The investigator should report the outcome of the pregnancy (independent of outcome, e.g., full term delivery, pre-term delivery, spontaneous abortion, induced abortion, stillbirth, death of newborn, congenital anomaly [including anomaly in a miscarried fetus, etc.] in accordance with the same reporting procedure as for SAEs. The date of outcome of the pregnancy, gestational age, date of birth and neonatal data etc., should be included in this information.

8.3.3 Expected Adverse Events

An adverse event (AE) is considered “expected” if:

- For approved and marketed drugs or devices, those adverse events are described in the approved Package Insert (Label).
- For investigational new drugs or devices, those adverse events are described in the FDA Investigator’s Brochure.
- In clinical research studies, information on expected adverse events is also summarized in the protocol and in the consent document. See section 9.1 for the list of expected adverse events related to the drug under study.

8.3.4 Unexpected Adverse Event

An adverse event (AE) is considered “unexpected” if it is not described in the Package Insert, Investigator’s Brochure, in the protocol, or in the informed consent document.

8.4 Adverse Event Characteristics

8.4.1 CTCAE Term

(AE description) and grade: The descriptions and grading scales found in the NCI Common Terminology Criteria for Adverse Events (CTCAE) version 5.0 will be utilized for AE reporting. All appropriate treatment areas should have access to a copy of the CTCAE version 5.0. A copy of the CTCAE version 5.0 can be downloaded from the CTEP web site. (<http://ctep.cancer.gov>)

8.4.2 Attribution of the AE

The investigator or co-investigator is responsible for assignment of attribution.

Definite – The AE is *clearly related* to the study [treatment/intervention].

Probable – The AE is *likely related* to the study [treatment/intervention].

Possible – The AE *may be related* to the study [treatment/intervention].

Unlikely – The AE is *doubtfully related* to the study [treatment/intervention].

Unrelated – The AE is *clearly NOT related* to the study [treatment/intervention].

8.5 Serious Adverse Event Reporting Guidelines

All serious adverse events (SAEs) and unanticipated problems (UPs), regardless of causality to study drug, will be reported to the Principal Investigator and also to the Coordinating Center. All SAEs and UPs must be reported to the Coordinating Center within 24 hours of first awareness of the event. Events should be reported using the Coordinating Center SAE form as available in the study database. A copy of the Coordinating Center SAE form should be sent to the Coordinating Center via fax at [contact] or via email to [contact] within 24 hours of the site’s knowledge of the event.

Principal Investigator Contact Information for SAE reporting:

[name]
Internal Medicine - Hematology/Oncology
University of Michigan
[name]
[name]
[name]
[contact]
[contact]
Email: [contact]

Follow-up information must also be reported within 24 hours of receipt of the information by the investigator.

All SAEs and UPs will be reported to the local IRBs per current local institutional standards.

The Coordinating Center will disseminate information regarding SAEs and UPs to the participating sites within 5 days of review of the information by the Coordinating Center's Principal Investigator (or designee in the event of extended absence) only in the case that the event(s) is believed to be related (i.e., possibly, probably, or definitely) to the study drug. The Coordinating Center will be responsible for reporting of events to the FDA and supporters, as appropriate (outlined below).

The University of Michigan acting as the Coordinating Center will be responsible for reporting to Ionis Pharmaceuticals by facsimile any Serious Adverse Event that occur during the SAE reporting period. The coordinating center will report the SAE within 24 hours of first awareness of the event (immediately if the event is fatal or life-threatening).

8.5.1 SERIOUS ADVERSE EVENT REPORTING TO THE FDA

It is the responsibility of the IND Sponsor to submit an IND for clinical trials conducted with investigational agents and to ensure that FDA and all participating investigators are promptly informed of significant new AEs or risks with respect to the investigational agent.

In this trial, serious unexpected adverse events believed to be definitely, probably or possibly related to the study treatment will be reported to the Food and Drug Administration via the MedWatch 3500A. The Coordinating Center, will coordinate with the IND Sponsor and/or designee for the reporting of any and all IND safety reports to the FDA as per the requirements outlined in 21 CFR 312.32.

8.6 Routine Reporting

All other adverse events such as those that are expected, or are unlikely or definitely not related to the study participation are to be reported annually as part of regular data submission.

